3.3 Benefits and Risks

Based on the venetoclax studies, the regimen is designed to escalate the dose of venetoclax rapidly and safely with a standard dose and schedule of LDC to optimize the opportunity for achieving a response and enable close subject monitoring. The dosing regimen will also enable interruptions and slower intra-subject dose escalation to target assigned dose if rapid tumor lysis is observed. Based on the ex vivo testing of primary subject AML samples that has shown significant variability among subjects, initial signs of leukemia response may occur at different doses of venetoclax when combined with LDC for different subjects.

Venetoclax was administered to 32 subjects with AML as monotherapy in Study M14-212. Safety data from 28 (87.5%) subjects who experienced adverse events of grade 3 and above, showed the most common events being febrile neutropenia (31.3%), malignant

neoplasm progression, (25.0%), hypokalemia, and pneumonia (21.9% each). Serious adverse events were reported for 27 (84.4%) subjects, including febrile neutropenia (9 subjects), malignant neoplasm progression (8 subjects), pneumonia (5 subjects), abdominal pain, sepsis, urinary tract infection, failure to thrive, renal failure acute, and hypotension (2 subjects each). All other events occurred in 1 subject each.

Study M14-212 has completed with efficacy data available for 32 subjects, the majority of them (30, 94%) with R/R AML. The ORR was 19% (6 of 32 subjects), with CR in 2 (6%) and CRi in 4 (13%) subjects. Anti-leukemic activity was observed in an additional 6 (19%) subjects.

For additional safety and efficacy data please refer to the current Investigator Brochure.²⁵

Considering the coronavirus (COVID-19) pandemic, the benefit and risk to subjects participating in this study has been re-evaluated. Subjects receiving venetoclax may be at an increased risk for COVID-19 infection or experience serious illness if infected. Management of these adverse events will be made on a case-by-case basis with consideration of benefit/risk. However, based on the population and disease being studied and the anticipation that COVID-19 related risks are not expected to differ substantially between study subjects and the broader population of subjects receiving treatment for AML, no change to the benefit/risk balance for subjects in this study is expected.

4.0 Study Objective

The primary objectives of the Phase 1 portion are to assess the safety profile, characterize PK, determine the dose schedule, the maximum tolerated dose (MTD), and the recommended Phase 2 dose (RPTD) of venetoclax (ABT-199/GDC-0199) in combination with LDC in treatment-naïve subjects with AML who are ≥ 65 years of age and who are not eligible for standard induction therapy due to co-morbidity or other factors.

The primary objectives of the initial Phase 2 portion of the study are to evaluate the preliminary estimates of efficacy including the overall response rate (ORR), and to characterize the toxicities of the combination at the RPTD.

The primary objective of Phase 2 Cohort C is to evaluate the ORR for subjects allowed additional supportive medications (strong CYP3A inhibitors) if medically indicated.

The secondary objectives of the initial Phase 2 portion and Phase 2 Cohort C are to evaluate leukemia response (rates of CR, CRi, PR, and MLFS), duration of response (DOR) and overall survival (OS).

Additional exploratory objectives of both phases of the study may be evaluated to find biomarkers that may serve as surrogates or predictors for clinical outcomes in future studies of venetoclax in AML.

5.0 Investigational Plan

5.1 Overall Study Design and Plan: Description

This is a Phase 1/2, open-label, non-randomized, multicenter study that will evaluate the PK, safety and efficacy of orally administered venetoclax combined with LDC in treatment-naïve subjects with AML \geq 60 years old and who are not eligible for standard induction therapy due to co-morbidity or other factors. This study is sponsored by AbbVie in collaboration with Genentech/Roche.

[figure not shown]
This study will consist of three distinct portions. The first portion of the study is a Phase 1, or dose-escalation portion, that will evaluate the safety and PK profile of venetoclax administered with LDC with the objective of defining the MTD and generating data to support a RPTD. A subsequent initial Phase 2 portion will evaluate if the RPTD has sufficient efficacy and acceptable toxicity to warrant further development of the combination therapy. Subsequently, Phase 2 Cohort C, will evaluate the ORR for subjects allowed additional supportive medications (strong CYP3A inhibitors) if medically indicated.

The study is designed to enroll up to approximately 42 subjects in Phase 1. For the initial Phase 2 portion, up to approximately 50 subjects will be treated at the RPTD and schedule

defined in the Phase 1 portion of the study. Phase 2 Cohort C will enroll approximately 20 subjects.

All efforts will be made to adhere to these specified enrollment numbers; however, recognizing the acute nature of the disease, it might not be possible to deny treatment to subjects in screening for ethical reasons or maintain individual subjects on therapy sufficiently long to evaluate safety or efficacy.

Figure 1. Overall Study Design

Biomarkers (such as cytogenetics, molecular markers, characterization of Bcl-2 and associated proteins or ex vivo testing of AML subject samples) that may be predictive of venetoclax activity will be assessed throughout the trial and may be used to enrich for subjects likely to respond to venetoclax.

Dosing Schedule Overview – Venetoclax – Phase 1 Portion

Venetoclax will be administered orally once daily (QD) on Days 2 through 28 of Cycle 1 of the 28-day cycle. Beginning with Cycle 2, venetoclax will be administered Days 1 through 28 of each 28-day cycle. Each dose of venetoclax should be taken with approximately 240 mL of water within 30 minutes after the completion of a meal, preferably breakfast. The dose should be administered at the same time each day. On days the subject is given LDC, venetoclax should be given prior to LDC. The regimen is designed to escalate the dose of venetoclax in combination with LDC rapidly toward the target dose to optimize the opportunity for achieving a response and enable close subject monitoring. The dosing regimen will also enable interruptions, reductions (if necessary) and a slower intra-subject dose escalation if rapid tumor lysis or other toxicities are observed.

The initial period, approximately one week, of therapy until the target dose of venetoclax is achieved is considered the venetoclax ramp-up period (Day 1 through Day 4, 6 or 7 of Cycle 1, based on the escalation steps in the cohort).

[figure not shown]
Dose modifications of venetoclax in the ramp-up period may be implemented for individual subject(s) at risk for TLS or any new adverse events > Grade 2. Dose reductions must follow original dosing schema. If the subject requires dose reductions or dose holds during the venetoclax ramp-up period, a discussion with the AbbVie medical monitor is required.

To mitigate the potential risk of TLS,³⁶ subjects will receive TLS prophylaxis prior to any venetoclax dose escalation in combination with LDC (See [Appendix E](#) for specific allopurinol and IV fluid dosing guidance). Subjects will be hospitalized during the ramp up period, with confinement recommended to begin by Study Day –1, and must occur by at least Day 1, through at least 24 hours after completion of the ramp-up period (e.g., Day –1 through Day 5 of Cycle 1 based on the escalation steps in Cohort C). Tumor lysis syndrome prophylaxis will be initiated in all subjects starting at least the day before the first dose of venetoclax. Refer to Section 6.1.8.2, Management of Tumor Lysis Syndrome, for the details on TLS prophylaxis, [Appendix E](#) – Recommendations for Initial Management of Electrolyte Imbalances and Prevention of Tumor Lysis Syndrome for procedures to follow, and [Appendix H](#) for information regarding how to recognize laboratory and clinical TLS.

If a subject develops any laboratory changes suggestive of TLS within the first 24 hours after either the first dose or during dose escalation, venetoclax dose escalation should be withheld or the dose should be reduced. Dose reductions and dose holds during the ramp-up period require notification of the AbbVie medical monitor as do any occurrence of clinical TLS.

[figure not shown]
Dosing Schemas for Phase 1

Figure 2. Dose Level –2 Cycle 1

[figure not shown]
* Cycle = 28 days. Venetoclax dose will be administered on Day 1 – Day 28 starting with Cycle 2, at the designated cohort dose of 200 mg.

Figure 3. Dose Level –1 Cycle 1

[figure not shown]
* Cycle = 28 days. Venetoclax dose will be administered on Day 1 – Day 28 starting with Cycle 2, at the designated cohort dose of 400 mg.

Figure 4. Dose Level 1 Cycle 1 (Starting Dose Level)

[figure not shown]
* Cycle = 28 days. Venetoclax dose will be administered on Day 1 – Day 28 starting with Cycle 2, at the designated cohort dose of 600 mg.

Figure 5. Dose Level 2 Cycle 1

[figure not shown]
* Cycle = 28 days. Venetoclax dose will be administered on Day 1 – Day 28 starting with Cycle 2, at the designated cohort dose of 800 mg.

Figure 6. Dose Level 3 Cycle 1

[figure not shown]
* Cycle = 28 days. Venetoclax dose will be administered on Day 1 – Day 28 starting with Cycle 2, at the designated cohort dose of 1200 mg.

Figure 7. Dose Level 4 Cycle 1

* Cycle = 28 days. Venetoclax dose will be administered on Day 1 – Day 28 starting with Cycle 2, at the designated cohort dose of 1600 mg.

Figure 8. Dose Level 5 Cycle 1

* Cycle = 28 days. Venetoclax dose will be administered on Day 1 – Day 28 starting with Cycle 2, at the designated cohort dose of 2000 mg.

Low-Dose Cytarabine Dosing (Phase 1 and 2)

LDC (20 mg/m²) will be administered subcutaneously for 10 consecutive days at the start of each cycle during both Phase 1 and Phase 2.

Dose Escalation and Modification Guidelines for Venetoclax – Phase 1

During Phase 1, modifications in the ramp-up period may occur based on tolerability of the first week dose escalation in earlier dose levels. Increases in starting dose and/or changes in the dosing increments may be implemented. The initial dose in subsequent cohorts may be lowered based on the tolerability, including the presence of signs of clinically significant laboratory or clinical tumor lysis. Dose escalation to the target dose may then occur in smaller increments. Decisions to modify the ramp-up period will be made by AbbVie following discussion between the investigators and AbbVie medical monitor. Historically, subjects receiving treatment for AML are at risk for developing TLS and accordingly TLS is an AESI in this protocol. If a subject experiences clinical TLS while receiving protocol therapy, AbbVie's medical monitor and safety team will review safety data (both pertaining to the individual subject and in aggregate) to determine if modifications to the first week dose escalation schedule or TLS prophylaxis are warranted.

Once 3 subjects are enrolled to a dose level, dose escalation or de-escalation decisions to the next designated dose level will be made after subjects have been evaluated to determine if each experienced a DLT during the first cycle of therapy or not. This will typically occur 28 ± 14 days from the last subject within a cohort starting therapy.

Subjects are enrolled in cohorts of three, and the first subject from the subsequent cohort should not begin their intended dosing regimen until it is declared by the sponsor that no DLTs have occurred during Cycle 1 of the previous cohort. All efforts will be made to adhere to these specified enrollment numbers (e.g., cohorts of three); however, recognizing the acute nature of AML, it might not be possible to deny treatment to subjects in screening for ethical reasons or maintain individual subjects on therapy sufficiently long to evaluate safety or efficacy. In the event that more than 3 subjects enroll into a cohort, only the first 3 subjects dosed and will be informative for defining the MTD. Should more than 3 subjects initially enroll into a dose level, subsequent subject data may be used to replace initial subjects if any of those subjects become non-evaluable due to non-adherence or other reasons.

For this trial, DLTs are defined as experiencing a CTCAE grade 4 toxicity, unless such events are in the common list of health events due to AML ([Appendix F](#)), or not recovering platelets to at least $25,000/\mu\text{L}$ and ANC to $500/\mu\text{L}$ within 14 days of the last dose of venetoclax unless such cytopenias are due to residual leukemia effect. Should 1 subject experience a DLT, an additional 3 subjects will be enrolled at the same dose level (a total of 6 subjects at this dose level). Should 2 subjects at a dose level experience a DLT, that dose level is considered too toxic. The dose level below the too toxic dose level is considered the MTD. Additional subjects are then enrolled at the MTD to bring the total number enrolled at the MTD to 6. If during this cohort expansion, a total of 2 subjects at this dose level also experience a DLT, this level would also be considered too toxic and the method continues thusly until the maximal dose level is achieved where 6 subjects can be treated through Cycle 1 and no more than one subject experiences a DLT. Additional subjects may be enrolled at the current dose level at the discretion of the AbbVie medical monitor, if enrolled subjects are not evaluable. In addition, significant

adverse events occurring after Cycle 1 in previous dose levels and ongoing PK assessments may inform dose escalation decisions and should such unanticipated occurrences necessitate a modification to the planned cohort dose assignments, decisions will be communicated in writing to all investigators.

Dose Escalation Guidelines

Number of Subjects with DLT	Dose Escalation
0 of 3	Begin enrollment in the next dose level
1 of 3	Enroll 6 subjects in current dose level
1 of 6 or < 33% DLTs	Begin enrollment in the next dose level
≥ 2 of 6 or ≥ 33% DLTs	Previous dose determined as the MTD or dose de-escalation

If a dose de-escalation occurs and < 33% of subjects enrolled experience a DLT at the reduced designated cohort dose, this dosing regimen will be declared the MTD. If ≥ 33% of the subjects enrolled at the reduced designated cohort dose still experience a DLT, dose de-escalation of the designated cohort dose regimen will continue to be explored.

The MTD will be defined as the highest designated cohort dose level (and corresponding ramp-up period regimen, if applicable) at which < 33% of the subjects enrolled experience a DLT.

[figure not shown]
Subjects should experience a DLT and/or complete at least 80% of indicated venetoclax and cytarabine dosing in the first cycle to be considered evaluable regarding dose modification decisions.

Transition from Phase 1 to Phase 2

Once the MTD is determined, enrollment into the dose escalation portion of the study will end. The dose level for the Phase 2 cohort will be communicated to all participating investigators prior to the start of Phase 2 enrollment. Subjects from the dose escalation portion of the study are not eligible for enrollment in the Phase 2 portion of the study.

Dosing Schema for Initial Phase 2

[figure not shown]
Figure 9. Dose Level 1 Cycle 1 (Starting Dose Level)

* Cycle = 28 days. Venetoclax dose will be administered on Day 1 – Day 28 starting with Cycle 2, at the designated cohort dose of 600 mg.

Dosing Schema for Phase 2 Cohort C

Figure 10. Phase 2 Cohort C**

* Cycle = 28 days. Venetoclax dose will be administered at the designated cohort dose of 600 mg on Day 4 – Day 28 of Cycle 1 and on Day 1 – Day 28 for all cycles starting Cycle 2.

** Applies to subjects enrolled in Amendment 2.

Dosing Schedule Overview – Venetoclax – Initial Phase 2 Portion and Phase 2 Cohort C

Once the MTD is declared, and the RPTD determined, a cohort of up to approximately 50 – 100 additional eligible subjects will be enrolled at the RPTD in order to further define the toxicity profile and to estimate the efficacy of the combination.

Subjects enrolled in the initial Phase 2 portion will receive the RPTD of venetoclax that will be administered orally once daily (QD) on Days 2 through 28 of Cycle 1 of the 28-day cycle. Beginning with Cycle 2, venetoclax will be administered Days 1 through 28 of each 28-day cycle. Cytarabine 20 mg/m²/QD will be administered on Days 1 – 10 of each cycle.

Subjects enrolled in Phase 2 Cohort C will receive venetoclax on Days 1 through 28 of each 28-day cycle, including Cycle 1. Cytarabine 20 mg/m²/QD will be administered on Days 1 – 10 of each cycle.

Each dose of venetoclax should be taken with approximately 240 mL of water within 30 minutes after the completion of a meal, preferably breakfast. The dose should be administered at approximately the same time each day. On days the subject is given LDC, venetoclax should be given prior to LDC. The regimen is designed to escalate the dose of venetoclax in combination with LDC rapidly toward the target dose to optimize the opportunity for achieving a response and enable close subject monitoring. The dosing regimen will also enable interruptions, reductions (if necessary) and a slower intra-subject dose escalation if rapid tumor lysis or other toxicities are observed.

The initial period, approximately one week, of therapy until the target dose of venetoclax is achieved is considered the venetoclax ramp-up period (e.g., Day 1 through Day 4 of Cycle 1 in Phase 2 Cohort C).

Dose modifications of venetoclax in the ramp-up period may be implemented for individual subject(s) at risk for TLS or any new adverse events > Grade 2. Dose reductions must follow original dosing schema. If the subject requires dose reductions or dose holds during the venetoclax ramp-up period, a discussion with the AbbVie medical monitor is required.

To mitigate the potential risk of TLS,³⁶ subjects will receive TLS prophylaxis prior to any venetoclax dose escalation in combination with LDC. Subjects will be hospitalized during the ramp-up period, Day –1 through 24 hours post highest cohort dose (e.g., Day –1 through Day 5 of Cycle 1 in Cohort C). Tumor lysis syndrome prophylaxis will be initiated in all subjects starting at least the day prior to the first dose of venetoclax. Refer to Section 6.1.8.2, Management of Tumor Lysis Syndrome, for the details on TLS prophylaxis, [Appendix E](#) – Recommendations for Initial Management of Electrolyte Imbalances and Prevention of Tumor Lysis Syndrome (TLS) for procedures to follow, and [Appendix H](#) for information regarding how to recognize laboratory and clinical TLS.

If a subject develops any laboratory changes suggestive of TLS within the first 24 hours after either the first dose or during dose escalation, venetoclax dose escalation should be withheld or the dose should be reduced. Dose reductions and dose holds during the ramp-up period require notification of the AbbVie medical monitor as do any occurrence of clinical TLS.

Option to Continue Venetoclax Treatment

Subjects enrolled in either Phase 1 or Phase 2 portion may discontinue LDC but may continue receiving venetoclax once daily as monotherapy for up to 4 years following the first dose of the last subject enrolled on study provided they complete LDC dosing, continue to tolerate venetoclax, have no evidence of disease progression, and do not meet any criteria for subject discontinuation (Section 5.4.1). Additionally, should a subject discontinue venetoclax or LDC due to reasons other than progression or unacceptable toxicity, subjects may be allowed to subsequently resume treatment with venetoclax and/or LDC upon discussion between the AbbVie medical monitor and the investigator.

For subjects that continue to derive benefit after this 4 year period, AbbVie will work with the investigator to evaluate options for continuation of venetoclax. Approval of a subject to transition to monotherapy and dose/schedule determination will also be based on review of other laboratory parameters and discussion between the AbbVie medical monitor and the investigator.

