5.6 Discussion and Justification of Study Design

5.6.1 Discussion of Study Design and Choice of Control Groups

Low-dose cytarabine is a commonly prescribed treatment within the United States for subjects who fulfill the entry criteria of this study. Venetoclax is undergoing testing in other clinical trials as a single-agent treatment for AML and in combination with other standard AML treatments. The ongoing single-agent study, Study M14-212, has

demonstrated that venetoclax has anti-leukemia activity for subjects with relapsed or refractory AML and therefore may be efficacious for subjects with previously untreated AML. This study consists of a Phase 1 portion to define the MTD and generate data to support a RPTD for the Phase 2 portion. The Phase 1 portion of the study is a dose escalation phase which will consist of up to 42 subjects who initiate therapy with venetoclax combined with cytarabine. In each cohort, a minimum of 3 and/or up to 6 subjects will be evaluated before making venetoclax designated cohort dose escalation decision. A subsequent Phase 2 portion will enroll approximately 50 subjects who will be administered venetoclax at the RPTD and schedule defined in the Phase 1 portion of the study. An additional Phase 2 cohort, Cohort C, will evaluate if the ORR for subjects enrolled with modified entry criteria and allowing additional supportive medications (strong CYP3A inhibitors) is substantially different than the ORR observed for subjects enrolled under the prior entry criteria in Phases 1 and 2. There are no direct control groups in this study although a recent historical control cohort of treatment naïve subjects age 65 and older with AML receiving LDC reported an 11% ORR utilizing the same response definitions.³⁰

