6.1.8.6 Determination of the MTD

If a single subject within a cohort experiences a DLT, a total of 6 subjects will be enrolled and dosed at the same dose level. If these additional subjects do not exhibit a DLT, dose escalation may proceed. If any of the additional subjects exhibits a DLT, then dose de-escalation may occur to interrogate lower dose levels. The MTD, if identified, will be defined at the highest dose level at which less than 2 of 6 subjects or < 33% of (if cohort is expanded beyond 6) subjects experience a DLT.

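### The Section 5.1 MTD definition divides DLTs by subjects enrolled instead of DLT-evaluable subjects, which can only dilute the rate and clashes with the protocol's own two-DLT rule

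*Protocol*

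**What the plan says.** Protocol Section 5.1, in the Phase 1 escalation guidance, has these provisions:

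- **MTD definition.** The highest level "at which < 33% of the subjects enrolled experience a DLT". The two de-escalation sentences before it use the same enrolled base.
- **Evaluability.** For dose decisions a subject must either have a DLT or "complete at least 80% of indicated venetoclax and cytarabine dosing in the first cycle to be considered evaluable".
- **Replacement.** More subjects may be added at a level "if enrolled subjects are not evaluable".
- **Surplus subjects.** When a cohort takes more than three, "only the first 3 subjects dosed and will be informative for defining the MTD". The sentence is garbled in the text available. The next one adds that "subsequent subject data may be used to replace initial subjects if any of those subjects become non-evaluable".
- **Count rule.** Two DLTs at a level make it too toxic. No population is named, and there is no limit to the first three.
- **Escalation table.** Escalation goes ahead at "1 of 6 or < 33% DLTs". Two or more of six, or 33% or more, means stepping back.
- **Cohort gate.** The next cohort waits until the sponsor has declared the previous one free of Cycle 1 DLTs.

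Section 6.1.8.6 restates the MTD as the highest level at which "less than 2 of 6 subjects or < 33% of (if cohort is expanded beyond 6) subjects experience a DLT". It does not say which subjects. Neither SAP part (efficacy or safety) names a DLT-evaluable set or a DLT table.

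**The concern.** A 3+3 verdict needs one numerator, one denominator and one cut-off. Here the formal definition counts everyone enrolled, while the surrounding text restricts dose decisions to evaluable subjects and replaces the others. The two bases do not err in both directions. A subject who leaves early without a DLT is not evaluable but still counts as enrolled, so early dropout makes a level look safer.

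The first-three sentence adds a second problem. It calls a treated, evaluable surplus subject uninformative for the MTD, although the count rule and the cohort gate would both take a DLT in that subject into account.

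The MTD is a Phase 1 primary objective, and under Section 6.1.8.7 the Phase 2 dose may not exceed it. A reader of the report should be able to tell which subjects it rests on.

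**Working it through.** **1. The plan's own cut-offs.** Rate = DLTs / subjects, acceptable if below 33%.
- 1/6 = 16.7%: acceptable, as the table says.
- 2/6 = 33.3%: not acceptable, as the table says.

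The count and percentage rules agree at six subjects. Every result below is the same if the cut-off is 1/3 instead of 33%.

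**2. Direction of the difference.** Let x be the DLTs, E the evaluable and N the enrolled subjects at a level. Evaluable subjects are a subset of enrolled ones, so E ≤ N. Every DLT subject is evaluable, so x is the same on both bases and x/N ≤ x/E. The verdicts differ when x/E ≥ 33% but x/N < 33%. The enrolled base is always the lenient one.

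**3. Two examples.**
- Two DLTs, six evaluable, seven enrolled: 2/6 = 33.3% (too toxic) against 2/7 = 28.6% (meets the Section 5.1 definition).
- Three DLTs, nine evaluable, ten enrolled: 3/9 = 33.3% (too toxic) against 3/10 = 30.0% (meets it).

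In both, the count rule in Section 5.1 says too toxic, so two written rules contradict each other. In the first example, Section 6.1.8.6 also points to too toxic if the seventh enrollee is only a replacement and six subjects count. In the second, both bases exceed six, so Section 6.1.8.6 goes to its percentage and does not say of whom.

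**4. What this could mean at 800 mg.** Efficacy SAP Table 2 lists only 600 mg and 800 mg for this study. Table 3 gives 92 treated in all and 82 at 600 mg, so 92 − 82 = 10 were treated at 800 mg. Protocol Section 5.6.1 says that per cohort "a minimum of 3 and/or up to 6 subjects will be evaluated". The evaluable and DLT numbers at 800 mg are not given. Taking 10 as enrolled and assuming 6 to 10 evaluable:

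| Evaluable | DLTs at which the bases disagree | Evaluable rate | Enrolled rate |
|---|---|---|---|
| 6 | 2 | 33.3% | 20.0% |
| 6 | 3 | 50.0% | 30.0% |
| 7 | 3 | 42.9% | 30.0% |
| 8 | 3 | 37.5% | 30.0% |
| 9 | 3 | 33.3% | 30.0% |
| 10 | none | – | – |

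Four DLTs fail on either base (4/10 = 40.0%).

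**5. The count rule beyond six.** Two DLTs among seven evaluable subjects is 2/7 = 28.6%. That is acceptable under the percentage in Section 6.1.8.6 but too toxic under the count rule in Section 5.1. Fixing the denominator alone would leave this open.

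**6. Surplus subjects.** Take five enrolled, all evaluable, with DLTs in the fourth and fifth. The first three give 0/3; all five give 2/5 = 40.0%. The replacement sentence does not help, because none of the first three is non-evaluable. But the cohort gate holds the next cohort, and the count rule calls the level too toxic. Escalation would be blocked in practice; the first-three sentence simply contradicts the rules that block it.

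**The case against.** The strongest reply is that the word enrolled is loose drafting and the intent is plain. Replacing non-evaluable subjects makes sense only if evaluable subjects are the base, and the count rule gives the cautious answer in every example above. The evaluability sentence concerns dose modification decisions and does not itself state an MTD rate. The first-three sentence is visibly garbled, perhaps only in the text as extracted. Phase 1 is over, so rewording guides no dosing decision, and a changed rule could look retrospective. The interim study reports, not available here, may already tabulate DLT-evaluable subjects. The SAP parts are cross-study plans, so their silence on a DLT set proves little.

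Most of this stands, and it limits the point to a minor one. It does not remove it. The formal definition and the de-escalation sentences say enrolled. The replacement of surplus-cohort subjects is only permitted, not required. The count rule contradicts the definition instead of interpreting it, and Section 6.1.8.6 moves to a percentage beyond six.

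A reader might infer something stronger: that Section 5.1 leaves three denominators open to choice, so that the sponsor could escalate on 0/3 while ignoring DLTs in surplus subjects. The documents do not support that. The cohort gate and the count rule would stop that escalation.

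**Conclusion.** The inconsistency is real and minor. The MTD definition and de-escalation rule use an enrolled base that can only lower the DLT rate relative to the evaluable base. They can then contradict the two-DLT rule in the same section. The first-three sentence conflicts with that rule and with the cohort gate.

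The size is one verdict at the margin, such as 28.6% against 33.3%, or 30.0% against 33.3%. With ten enrolled at 800 mg, the bases could disagree only at two or three DLTs, and only if some of the ten were not evaluable. That rests on the subtraction 92 − 82 and an assumed 6 to 10 evaluable.

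A reader might also infer that the MTD was wrongly set or that 800 mg was misjudged. Nothing shows this. The ten subjects could be surplus, replacements or both, and their DLT count is unknown. The 600 mg Phase 2 dose and past dosing are unaffected. What is affected is how the MTD is defined and reported.

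**What to change.** - In the Section 5.1 MTD and de-escalation sentences, replace enrolled with DLT-evaluable, meaning a DLT or at least 80% of Cycle 1 dosing of both drugs. Name the same base in Section 6.1.8.6.
- Count all DLT-evaluable subjects at the level, and limit the first-three sentence to the timing of escalation.
- State that beyond six evaluable subjects the below-33% rule in Section 6.1.8.6 replaces the two-DLT count.
- In the Phase 1 report, tabulate enrolled, DLT-evaluable and DLT numbers at 600 mg and 800 mg, and say whether the MTD conclusion holds on both the enrolled and the evaluable base. Showing both answers any charge that the rule was chosen after the fact. If the interim reports already do this, only the wording remains.

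The cost is a few sentences of protocol text and one table from existing Phase 1 data. No new data are needed and dosing does not change.
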